## **13.2 Informed consent**

Patients will be given a patient information sheet about the trial and the anticipated benefits, where, among other information, the potential risks associated with the protocol procedures will be explained. The investigator or a person designated by the investigator will inform the patient or the patient's legally acceptable representative. The language used will be as non-technical as possible, and the patient will not unduly be influenced to participate in the trial.

Written informed consent must be obtained from every patient prior to any procedures being done specifically for the study. For illiterate patients, study information is given in the presence of an impartial, literate witness, who will read the information sheet to the patient or will witness the complete reading of the information sheet to the patient. The patient will give consent by thumb printing the ICF. The witness states that free, informed consent has been given by his/her signature on the ICF. An original or a photocopy of the signed informed consent form will be provided to the patient or to the patient's legally acceptable representative, depending on locally applicable regulations. A signed original will be kept with the patient's medical records at the site.

Participants will be informed that screening includes collecting sputum samples for smear and culture, chest X-ray and ECG registration, blood and urine samples, pregnancy testing, if applicable, and testing for HIV. Patient will be encouraged to receive their HIV results but may choose not to be informed. HIV seropositive individuals will be referred to the local HIV services. Participants will be informed that agreeing to be screened does not mean that they must join the trial, however that participation in the trial will require good adherence. Patients will be informed that any from the study at any time, and that withdrawal will have no negative effects on them receiving standard care afterwards.

The site will document the name and position of those study personnel at the site who have received appropriate Good Clinical Practice (GCP) training in advance are responsible for obtaining informed consent. No other staff will perform the informed consent process.

The informed consent template will be provided to the investigator by the Sponsor. If any modifications to the informed consent form are proposed by the site, the consent form must be submitted to the Sponsor for approval prior to submission to the ethics committee. The informed consent form will be revised whenever new important information becomes available. Each consent form revised during the course of the study will need to be reviewed by an ethics committee. The ICF can only be used after approval of the ethics committee. After approval of a revised informed consent, all active participants must sign the revised informed consent form to be able to continue study participation.

# 13.3 Exclusion of particular groups

Minors below 18 years are excluded from the study. TB in children is different in diagnosis and disease course from adult disease. Therefore, this age group will not participate in this trial.

# **13.4 Vulnerable participants**

Patients who are unable to give free, informed consent (e.g. mentally impaired persons, prisoners) will be excluded from the trial, as their uncoerced agreement to study participation and procedures cannot be ascertained, and compliance may be suboptimal.

# 13.5 Procedures to assign participants to treatment groups

Patients who have given informed consent and who have been found eligible for participation (meeting all inclusion criteria and no exclusion criterion) based on results from screening visit, will be randomly assigned to one out of five treatment arms with a 1:1:1:1:1 allocation. Randomization must be performed when all screening results are available but not before eligibility for study participation is proven.

Randomization will be performed through centralized assignment of patients by means of an Interactive Web Response System (IWRS), a web-based randomization system. Patient characteristics will be used to balance the composition of the treatment arms with regards to prognostic factors.

These characteristics will be:

- site
- HIV status
- bacterial load in sputum as measured by GeneXpert cycle threshold

# **13.6 Methods of avoiding bias**

This study will be open-label, patients and physicians will be aware of treatment allocation. To ensure unbiased assessment of efficacy endpoints, the personnel assessing patients' outcomes, like the microbiology laboratory staff or the sponsor medical expert discussing the possibility of recurrent disease, will remain blinded to treatment assignment throughout the whole study. Every effort will be made to maintain this blinding.

Further, there will not be any cumulative summary of study data by randomized treatment arms generated, except for data to be provided to the independent data safety monitoring board (DSMB) by the unblinded statistician. Such analysis may not be distributed outside of the DSMB.

Determination of MICs for the experimental treatment allocated to the patients will only be made after all other assessments of patient samples have been completed in the respective laboratory or will be done at a different specialised laboratory.

# **13.7** Participant withdrawal

A patient may decide to withdraw consent and therefore withdraw from the trial at any time and for any reason. The investigator may also withdraw a patient from study treatment or the entire trial for any of the following reasons:

- A major protocol violation caused by the patient
- If, for any reason, the investigator concludes that continued participation in the trial would not be in the participant's best interest.
- Requires medication that is prohibited by the protocol

The investigator will also withdraw a patient upon request of the Sponsor or if the study is terminated. If a serious adverse event occurs, the Principal Investigator will discuss it with the sponsor. A patient who is discontinued due to an AE, will be followed up as described under "Adverse Events".

In general, patients who withdraw or are withdrawn from treatment (but still maintain consent to continue in the study) shall continue to follow study assessments as laid down in the schedule of events, in order to make them evaluable in the ITT population.

When a patient is withdrawn from the study, the reason(s) for withdrawal shall be recorded by the investigator on the relevant page of the case report form (CRF). When a patient withdraws from the study on his/her own decision, it is up to the patient to provide a reason thereof. The investigator shall at least ask for the reason and point out that the collection of all withdrawal reasons is of great importance for the sponsor from a medical and scientific point of view.

On the date of withdrawal and in the interest of participants' safety, if consent to this is still maintained, participants should have all assessments scheduled for Day 112 (WK16) completed at the day they leave the study. These include vital signs, complete physical examination, including neurological examination and vision testing, safety lab, 12-lead ECG, concomitant medication and assessments of AEs.

Recent safety laboratory results should be available to make sure that no adverse findings are missed that could put the participant at risk. In a female participant of childbearing potential, a serum pregnancy test should be requested, if possible.

If a continuation following the schedule of assessments is not possible, and if the participant agrees, a follow-up visit should be scheduled 14 days (+/-4 days) after withdrawal. During this visit all procedures as described in section 10.5.3, page 48, "Follow-up Period", of the protocol should be carried out, i.e. vital signs, symptom related physical examination, follow-up of former AEs and assessments of new AEs, incl. blood tests to follow up on past abnormal results and new AEs, as per investigators discretion.

For patients who withdraw from the study, every attempt should be made to perform all or as many as possible of the follow-up assessments.

Patients who do not return for final assessments will be contacted by site personnel in an attempt to complete the follow-up assessments.

All attempts gearing towards the completion of the study visits should be documented in the patients's study file.

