#### FU 4 at WK52: all patients (Day 364 ± 7 days): all patients

All reasonable efforts should be made to achieve on-site visits being conducted. Should this not be possible, a home visit by a study team shall be performed, or, if this is again not possible, telephonic visits will be conducted to obtain health status, information on TB treatment outcome and eventual re-treatment, and pregnancy status if the patient is a woman of childbearing potential.

Administrative & regulatory		• N/A
Clinical		
 
Physical examination, vital signs at FU 1 (WK18); at FU 2-4 (WK26, WK38, WK52) symptom orientated physical examination only or to follow up on (S)AEs
 
Neurological examination/vision testing at FU 1 (WK18); at FU 2-4 (WK26, WK38, WK52) symptom orientated neurological examination only or to follow up on (S)AEs
 
Concomitant medication
 
Adverse events
 

Laboratory	Blood	
 
Safety laboratory (blood sample of 9.5mL) at FU 1 (WK18)
 
Serum pregnancy test (blood sample of 7.5mL), if female of childbearing potential at FU 1 (WK18) only
 

	Urine	Urinalysis at FU 1 (WK18) only
Microbiology		
 
Spot sputum (2 sample)
 
Ziehl-Neelsen smear from concentrated sample
 
Culture in BD MGIT liquid media
 
Culture on LJ solid media
 
Analysis by MBLA and/or sputum LAM, if capacity/budget permits
 

Study drugs		• Standard of care TB treatment from government health system outside of the study, if patient did not meet the definition for sustained culture conversion by week 08.

Protocol No: PanACEA - DECODE – 01/ LCB01-0371-20-2-02 Protocol Version No: V2.1, dated 08 September 2021

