#### 12.6.3 Prohibited medication: anti-tuberculosis agents

Use of drugs with an action on MTB complex, in addition to study treatment, is prohibited while participants are receiving study treatment in both groups, intervention and control arm. This includes, but is not limited to *amikacin and other aminoglycosides, cycloserine, EMB, INH, LZD, para-aminosalicylic acid, RIF, rifabutin, rifapentine pyrazinamide, streptomycin, kanamycin, thioacetazone, capreomycin, fluoroquinolones, and thioamides*. Significant concomitant use of one or more of these agents will be evaluated by the sponsor medical expert and may lead to exclusion of the patient from treatment. Excluded patients will be taken off-IP and will be follow-up according to protocol. These patients' data will be analysed in an ITT-analysis.

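### Protocol 13.7 allows removal from the whole trial for needing a prohibited drug, while 12.6.3, 12.6.5 and 12.6.7 keep such patients in follow-up; the passages must be reconciled

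*Protocol*

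**What the plan says.** Protocol 13.7 sets out the investigator's power: "The investigator may also withdraw a patient from study treatment or the entire trial for any of the following reasons". Three reasons follow: "A major protocol violation caused by the patient"; an investigator's judgement that staying in the trial is not in the participant's interest; and "Requires medication that is prohibited by the protocol".

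Protocol 12.6.3 covers non-study anti-tuberculosis drugs. If their use leads to exclusion from treatment, "Excluded patients will be taken off-IP and will be follow-up according to protocol. These patients' data will be analysed in an ITT-analysis". Section 12.6.7 (serotonin agonists) says the same. Section 12.6.5 (QT-prolonging drugs) promises follow-up but does not mention ITT.

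Protocol 13.6 confirms who is blinded: "This study will be open-label, patients and physicians will be aware of treatment allocation".

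Section 13.7 also contains safeguards:

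- Patients withdrawn from treatment who keep their consent are, in general, to continue the scheduled assessments so that they can be evaluated in the ITT population.
- Patients leaving the study should have the Week 16 assessments that day, if they consent, including neurological, vision and laboratory tests.
- If the schedule cannot be continued and the patient agrees, there is one visit 14 days (±4) after withdrawal.
- For those who withdraw from the study, as much follow-up as possible should be attempted.

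The 14-day visit is first given all the procedures of 10.5.3. It is then narrowed: "i.e. vital signs, symptom related physical examination, follow-up of former AEs and assessments of new AEs", with blood tests to follow up past abnormal results and new adverse events, at the investigator's discretion.

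**The concern.** The same event can lead either to continued follow-up or to removal from the trial, and a site would comply with the protocol either way. The choice lies with someone who knows the dose. A prohibited drug may be needed because of illness or toxicity, so removal could be associated with arm and with outcome. Needing such a drug is not a withdrawal of consent.

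A removed patient who has taken a dose still belongs to the ITT population as Protocol 15.2.1 and SAP 6.1 define it. What is lost is the data after removal. In arms of 15, a few losses of this kind could shift a comparison between doses.

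Patient-caused protocol violations raise a related but weaker point. Section 12.6 has no rule for them, so nothing is contradicted. Removal still sits badly with an ITT population, because the plan already has the adequate adherence population to set aside ineligible patients and those who missed too many doses (Protocol 15.2.2, SAP 6.3).

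**Working it through.** **1. Prohibited-drug rules side by side**

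| Protocol section | Effect on study treatment | Follow-up stated | ITT stated |
|---|---|---|---|
| 12.6.1 enzyme-altering drugs | may be stopped | no | no |
| 12.6.3 anti-TB drugs | off drug if excluded | yes | yes |
| 12.6.5 QT-prolonging drugs | off drug if excluded | yes | no |
| 12.6.6 MAO drugs | may be excluded from treatment | no | no |
| 12.6.7 serotonin agonists | off drug if excluded | yes | yes |
| 12.6.4, 12.6.8 | prohibited; no withdrawal rule | no | no |
| 13.7, any prohibited drug | treatment **or entire trial** | scheduled if off treatment; best effort if off study | only if off treatment |

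The direct contradiction is with 12.6.3, 12.6.5 and 12.6.7. No part of 12.6 provides for removal from the trial.

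**2. Which analyses would lose data**

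- *Primary efficacy.* SAP 10 excludes TTP data collected after premature discontinuation of study medication. Keeping these patients in follow-up adds nothing to that model.
- *Relapse.* Protocol 9.2.2 and SAP 11.2 restrict it to patients who complete 16 weeks and convert early. A patient removed before then is already outside it.
- *Culture conversion.* SAP 12.1 uses Kaplan-Meier and Cox methods. SAP 11.4 states no censoring rule; I assume censoring at the last culture. Both methods need censoring that is unrelated to prognosis, which is what selective removal would undermine.
- *Solid-media status and later safety.* SAP 12.5 does not replace missing data, so later results would simply be absent.

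**3. Size**

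The plan's own figure is up to 3 drop-outs per group of 15 (Protocol 15.1): 3/15 = 20%, leaving 12. The standard errors in that section concern logCFU and are not used here.

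Let x successes be observed and k of 15 patients be unobserved. The arm proportion then lies between x/15 and (x + k)/15, a range of k/15. If two compared arms each lose k, the range for their difference is 2k/15.

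| k per arm | Range, one arm | Range, difference |
|---|---|---|
| 1 | 1/15 = 6.7 points | 2/15 = 13.3 points |
| 2 | 2/15 = 13.3 points | 4/15 = 26.7 points |
| 3 | 3/15 = 20.0 points | 6/15 = 40.0 points |

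These are limits, not expected biases.

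**4. The 14-day visit**

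FU 1 is on Day 126 ±4, and 126 − 112 = 14 days after the end of treatment, the same spacing as the post-withdrawal visit. Protocol 10.5.3 gives FU 1 a physical examination, neurological and vision testing, safety laboratory, urinalysis and sputum culture. The narrowed list in 13.7 omits neurological and vision testing, urinalysis and sputum, and makes bloods discretionary. Neuropathy and cytopenias are components of the primary safety endpoint (Protocol 9.1.1). The main adverse-event tables count onsets up to 14 days after treatment (SAP 13.1.2), so for a patient who leaves when treatment stops, this visit falls at the edge of that window.

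**The case against.** The strongest reply is that 13.7 already makes continued assessment the default for patients off treatment and asks for vigorous follow-up of the rest. That is true and narrows the point. It does not close it, because the firm default covers withdrawal from treatment. For withdrawal from the study, the text asks only for attempts.

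A second reply is that the investigator does not act alone: 12.6.3 and 12.6.5 to 12.6.7 refer significant use of these drugs to the sponsor medical expert. That stands for exclusion from treatment. Section 13.7 attaches no such step to removal from the trial on this ground.

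Four stronger readings are tempting and not supported:

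- *That outcome data are lost selectively.* The clause is permissive and no rate is given. Selective loss is a risk.
- *That neuropathy and cytopenias are generally sought less in patients who withdraw.* The exit assessments include neurological, vision and laboratory tests. The gap concerns one later fallback visit, whose list is ambiguous because it also invokes all of 10.5.3.
- *That 9/15 converters (60%) would become 9/12 (75%).* Kaplan-Meier gives 75% only if all three lost patients are censored before any conversion and the other three non-converters are followed throughout. The solid-media and relapse tabulations keep lost patients in their own categories.
- *That 20 or 40 points is the likely effect.* Three per arm covers drop-outs of every kind, and 40 points needs three losses in both arms with opposite extremes.

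**Conclusion.** The contradiction over prohibited drugs is real, confined to one trigger and three subsections of 12.6, and worth removing because it costs little. For patient-caused violations the point is consistency with ITT. A reader might infer that 12.6 protects those patients too; it has no rule on violations as such.

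What is exposed is mainly culture conversion and later safety. Each loss is 6.7% of an arm, and the 20-point range at three losses is an upper illustration. The conclusion assumes that some patients would be removed from the trial under this clause and that best-effort follow-up would not recover all their data; the documents give no basis for estimating either. No sample-size figure changes. The 14-day visit list is a separate, smaller inconsistency.

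**What to change.** - Reconcile Protocol 13.7 with 12.6 so that needing a prohibited drug, or a patient-caused protocol violation, does not by itself end follow-up and data collection while consent is maintained. Whether study treatment stops stays with the existing clinical rules, on which this point takes no position.
- Report withdrawal from treatment and withdrawal from the trial separately, by arm and reason. SAP 7.3 already tabulates timing and reasons for losses, but shell Table 1.2 has a single early-discontinuation row. Separate reporting would also show how often the best-interest ground, which this change leaves alone, leads to removal from the trial.
- Reconcile the 14-day post-withdrawal list in 13.7 with the FU 1 list in 10.5.3, so that components of the primary safety endpoint are ascertained alike in those who withdraw and those who complete.

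The cost is a wording change in the protocol, an extra row or two in one table, and a few more visits of a kind the schedule already provides for.

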# 13.8 Adjustment of sample size during the study

The number of patients, who withdraw or are withdrawn from the study for any reason after intake of at least one dose of study medication will be monitored by the Sponsor. If dropouts due to withdrawal are higher than expected, the sample size will be reviewed and might be revised by the responsible biometrician. Due to these revisions, adjustments to recruitment numbers might be necessary, which could lead to recruitment of more participants than currently planned.

# 13.9 Safety: expedited safety data review

An independent data safety monitoring board (DSMB) will be convened for the trial. The DSMB will review safety data at regular intervals as defined in the DSMB Charter, but will also perform expedited review if the following conditions are met:

- Three or more patients experience a grade 3 or higher AE (CTCAE 5.0) in the same organ system that are at least possibly related to one of the study drugs, and qualify as "unexpected" by being more severe than in previous experience with the drug in question.
- Two or more patients experience a grade 4 or higher AE (CTCAE 5.0) in the same organ system that are at least possibly related to one of the study drugs, and qualify as "unexpected" by being more severe than in previous experience with the drug in question.
- One patient experiences a grade 5 AE (death) that is at least possibly related to one of the study drugs

# 13.10 Additional safety considerations: individual patient stopping criteria for safety

• Hepatotoxicity stopping criteria: these follow the FDA guidance on evaluation of druginduced liver injury [66]. More detail on patient management in case of liver toxicity including intensifying the assessment schedule, is provided under 20.1, page 93.

A patient should discontinue study drug if:

- ALT or AST >8xULN
- ALT or AST >5xULN for more than 2 weeks
- ALT or AST >3xULN and (total bilirubin (TBL) >2xULN or INR >1.5

- ALT or AST >3xULN with the appearance of fatigue, nausea, vomiting, right upper quadrant pain or tenderness, fever, rash, and/or eosinophilia (>5%)
- As soon as symptoms resolve and elevated ALT/AST are below 2x ULN, reintroduction of study treatment is to be discussed with the sponsor medical expert. Study treatment will be reintroduced (all drugs simultaneously). Close, at least biweekly monitoring of symptoms and laboratory parameters is needed to identify repeated DILI. Should this occur, the study regimen will be permanently stopped and the participant be continued on a regimen that is considered non-toxic.
- All participants who discontinue study treatment should be followed up as described for follow-up of adverse events classified as "severe" (grade 3 and above).
- ECG stopping criterion: Participants will stop treatment if their on-treatment ECG shows a prolongation of the Fridericia corrected QT interval (QTcF) on average in triplicate ECGs to grade 3 as defined under 14.6.

In this case, the patient will be hospitalized and monitored closely with at least daily ECGs until the abnormality abates. Study drugs and other potentially offending drugs will be withheld. Blood electrolytes (mainly Mg+, Ca++, K+) will be measured and abnormalities corrected, after discussion with the sponsor medical expert.

As soon as the AE improves to grade 2 or less, study drugs might be restarted in close discussion with the sponsor medical expert, unless QTcF prolongation resulted in dangerous arrhythmias (grade 4 QTcF prolongation as defined under 14.6 *Table 2* – in this case, the patient will be discontinued from study treatment..

 Neuropathy stopping criterion: Participants will stop treatment with DZD in case they develop clinically significant signs of motor or sensory neuropathy, i.e. loss of muscle strength, loss of sensation, loss of vibration sensitivity, or loss of visual acuity or colour vision.

In this case, treatment with BDQ, DLM and MXF may continue as scheduled. Since neuropathy may be associated to MXF in rare events, a discontinuation of MXF may be advised in severe cases of neuropathy or if neuropathy does not improve after DZD is discontinued.

• Hypertension (tyramine pressor effect) stopping criterion:

